7.3 Definitions of Non-Serious Adverse Events

Adverse events that do not meet the definitions for serious adverse events (SAEs) are non-serious AEs. Subjects should be instructed to report any AE that they experience to the investigator.

7.4 Definition of Serious Adverse Event

An SAE is any experience that suggests a significant hazard, contraindication, side effect, or precaution. This includes any experience that:

- Results in death
- Is acutely life-threatening
- Requires in-patient hospitalization or prolongs the existing hospitalization
- Results in persistent or significant disability/incapacity
- Is a congenital anomaly/birth defect
- Requires medical or surgical intervention to prevent one of the outcomes listed above

Examples of such medical events include allergic bronchospasm requiring intensive treatment in an emergency room or at home, blood dyscrasias or convulsions that do not result in in-subject hospitalization, or the development of drug dependency or drug abuse. This definition includes concurrent illness or injuries, exacerbation of pre-existing conditions and AEs occurring as a result of drug withdrawal, abuse or overdose. Serious adverse events observed during all periods of a clinical study after the first dose of IP (Day 1) have been administered, are to be recorded, including those occurring during a period without study medication and whether or not the AE is judged to be related to the study medication.

7.5 Hospitalization

Reported adverse events associated with hospitalization or prolonged hospitalizations are considered serious. Any initial admission (even if less than 24 hours) to a healthcare facility

meets these criteria. Admission also includes transfer within the hospital to an acute/intensive care facility.

Hospitalization does not include the following:

- Rehabilitation facility
- Hospice facility
- Respite care (caregiver relief)
- Skilled nursing facility
- Nursing homes
- Routine emergency admission
- Same day surgeries

Hospitalization or prolongation in the absence of a precipitating, clinical adverse event (e.g., for work-up of persistent pre-treatment abnormality) is not in itself a serious adverse event.

Diagnostic and therapeutic noninvasive procedures, such as surgery, should not be reported as adverse events. However, the medical condition for which the procedure was performed should be reported if it meets the definition of an adverse event. For example, an acute appendicitis that begins during the adverse event reporting period should be reported as an adverse event and the resulting surgical intervention should be recorded as a treatment of that adverse event.

7.6 Pregnancy

If a subject becomes pregnant during the study or up until 30 days after the last dose of IP (i.e., the final clinical visit), the Investigator must notify D. Western Therapeutics, Inc. or its representative immediately and within 24 hours of learning of its occurrence by completing a Pregnancy Report Form and forwarding to D. Western Therapeutics, Inc. or its representative. The pregnancy should be followed to determine the outcome, including spontaneous or voluntary termination, details of the birth, and the presence or absence of any birth defects, congenital abnormalities, or maternal and/or newborn complications. Any complications during pregnancy should be recorded as an AE and may constitute an SAE if they fulfill any of the specified criteria for an SAE. If upon outcome, the pregnancy meets one of the serious criteria (e.g. spontaneous miscarriage, congenital anomaly, or birth defect), it will then be considered an SAE and full details will be requested. These events will not be included in the clinical study report, but will be maintained in the clinical study files.

7.7 Definition of Unexpected Adverse Events

An AE is considered an unexpected AE if it is not mentioned in the Investigator's Brochure (IB), or if it is of greater frequency and/or severity than that mentioned in the IB, in the judgment of the Medical Monitor.

7.8 Definition of Relationship of Adverse Event to IP

The investigator's assessment of causality must be provided for all adverse events (serious and non-serious). The investigator must record the relationship and report such an assessment in

accordance with the serious AE reporting requirements, if applicable. An investigator's causality assessment is the determination of whether there exists a reasonable possibility that the investigational product caused or contributed to the adverse event. If the investigator does not know whether or not the investigational product caused the event, then the event will be handled as "related to investigational product" for reporting purposes, as defined by D. Western Therapeutics, Inc. If the investigator's causality assessment is "unknown but not related to investigational product," this should be clearly documented in study records.

In addition, if the investigator determines a serious adverse event is associated with study procedures, the investigator must record this causal relationship and report such an assessment in accordance with the serious adverse event reporting requirements, if applicable. The categories are as follows:

0=Unrelated: No temporal association, or the cause of the event has been

identified, or the drug, biological, or device cannot be

implicated.

1=Possibly Related: Temporal association, but other etiologies are likely to be the

cause; however, involvement of the drug, biological, or device

cannot be excluded.

2=Probably Related: Temporal association, other etiologies are possible, but

unlikely.

3=Definitely Related: Temporal association and no other etiologies possible.

7.9 Documentation of Severity of Adverse Events

All adverse events will be examined to determine severity. The categories are as follows:

Mild: Awareness of sign, symptom, or event, but easily tolerated.

Does not interfere with subject's usual function.

Moderate: Discomfort enough to cause some interference with usual

activity and may warrant intervention.

Severe: Incapacitating with inability to do usual activities or

significantly affects clinical status, and warrants intervention.

Life-threatening: Immediate risk of death.

7.10 Reporting Serious Adverse Events

SAEs (this refers to any AE that meets one or more of the aforementioned serious criteria) occurring after the subject receives the first dose of IP (Day 1) will be reported to D. Western

Therapeutics, Inc. or its representative, followed until the event resolves or stabilizes, the subject's final visit or study completion (Day 28), or within 30 days of the last administration of IP, whichever comes first.

SAEs, and all deaths occurring within the study population, whether considered to be drug-related or not, will be reported using the SAE Report Form within 24 hours of knowledge of the occurrence to D. Western Therapeutics, Inc. or its representative.

This can be done by emailing a completed SAE Report Form to:

Name: [name]

Title: Drug Safety Specialist Consultant

Company: Safety Sphere, LLC (www.safety-sphere.com)

Email: [contact]

Office [contact] Office [contact]

When the initial report is made verbally or by telephone to D. Western Therapeutics, Inc. or designee, the SAE Report Form must be emailed within 24 hours according to the instructions above.

The investigator will be requested to supply detailed information regarding the event at the time of the initial contact. All SAEs (initial and follow-up information) must be reported to the reviewing Institutional Review Board/Ethics Committee, according to their reporting requirements, and a copy of that report must be forwarded to D. Western Therapeutics, Inc. or its representative. D. Western Therapeutics, Inc. (or designee) will report all Suspected Unexpected Serious Adverse Reactions (SUSARs) to Regulatory Authorities within 7/15 days of receipt depending on reporting requirements.

SAEs that come to the attention of the investigator within 30 days following the final study visit or Day 28 will be reported to D. Western Therapeutics, Inc. or its representative within 24 hours of knowledge of the occurrence.

7.11 Serious Adverse Event Follow-Up

For all SAEs, the investigator must submit follow-up reports to D. Western Therapeutics, Inc. or designee, regarding the subject's subsequent course until the SAE has subsided, or until the condition stabilizes (in the case of persistent impairment), the subject dies, or within 30 days of the last administration of IP, whichever comes first.

8. STATISTICAL PLAN

8.1 Sample Size

The sample size is driven by interest in the IOP lowering effect of H-1337. The study is designed to test whether one or more concentrations of H-1337 are non-inferior to the timolol control in the reduction of IOP. As benefit is represented by a negative number, non-inferiority

is achieved when the upper limit of the confidence interval of the difference in treatment (H-1337 minus Timolol) is strictly lower than the non-inferiority margin.

A sample size of 45 subjects per group will allow for at least 90% power to establish non-inferiority of H-1337 over Timolol based on a non-inferiority limit of -2 mmHg, a standard deviation of 3.0 mmHg and a 1-sided t-test (alpha=0.05).

Assuming that 10% of the subjects will not be eligible in the ITT population, a total of 50 subjects per group is required.

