8.3 Subject Population(s) for Analysis

All subjects who receive IP and at least one dose will be evaluable for the safety analysis. For efficacy considerations, the primary analysis population will be the intent-to-treat (ITT) population. All randomized subjects will be evaluable for the ITT analyses. Subjects who receive study medication, satisfy pre-randomization inclusion/exclusion criteria, and who complete at least one on-therapy study visit will be evaluable for a per protocol (PP) population analysis. Individual subject visits and data points that do not satisfy protocol criteria may be excluded from PP analyses. Evaluability will be determined prior to unmasking of treatment assignments.

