3.3 Sample Size Justification

The sample size is driven by interest in the IOP lowering effect of H-1337. The study is designed to test whether one or more concentrations of H-1337 are non-inferior to the timolol control in the reduction of IOP. As benefit is represented by a negative number, non-inferiority is achieved when the upper limit of the confidence interval of the difference in treatment (H-1337 minus Timolol) is strictly lower than the non-inferiority margin.

A sample size of 45 subjects per group will allow for at least 90% power to establish non-inferiority of H-1337 over Timolol based on a non-inferiority limit of 2 mmHg, a standard deviation of 3.0 mmHg and a 1-sided t-test (alpha=0.05).

Assuming that 10% of the subjects will not be eligible in the Intent-to-Treat (ITT) population, a total of 50 subjects per group is required.

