4.14 Interim Analysis

No interim analysis is planned.

5 Summary of Changes from the Protocol

The sample size section of the protocol refers to a non-inferiority limit of 2, while the thresholds of 1.5 and 1 will be used in the analysis of the primary endpoint.

In the protocol, the primary endpoint refers to Day 28 only. In the SAP, the primary endpoint is concluded as non-inferior based on the 5 time points at Day 28 and the 4 on-treatment time points at Day 1.

6 List of Programming Summary & Analysis Tables

Confidential

The list and layout of the summary tables and listings will be described in a separate document.

7 Appendices

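### Protocol 8.1 prints the non-inferiority limit with the wrong sign (-2 mmHg) and allows 10% loss from an ITT set that includes everyone randomized

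*Protocol*

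**What the plan says.** Protocol 8.1 sets the direction of the comparison: "As benefit is represented by a negative number", and non-inferiority holds when the upper confidence limit of "the difference in treatment (H-1337 minus Timolol) is strictly lower than the non-inferiority margin". It then claims at least 90% power with 45 subjects per group, "based on a non-inferiority limit of -2 mmHg", with SD 3.0 mmHg and a one-sided t-test at 0.05. SAP 3.3 gives nearly the same paragraph, but "based on a non-inferiority limit of 2 mmHg". SAP section 5, which lists departures from the protocol, says: "The sample size section of the protocol refers to a non-inferiority limit of 2", and adds that thresholds of 1.5 and 1 will be used in the analysis. The protocol synopsis speaks of a difference of 2.0 mm Hg, unsigned.

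On loss, Protocol 8.1 goes from 45 to 50 per group: "Assuming that 10% of the subjects will not be eligible in the ITT population". SAP 3.3 makes the same allowance. Protocol 8.3 states: "All randomized subjects will be evaluable for the ITT analyses". SAP 3.4.2 likewise defines ITT as all randomized subjects. Protocol 8.5 and SAP 4.2 say that missing data are not imputed.

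The tests themselves (Protocol 8.4, SAP 4.3) compare the upper limit of a two-sided 95% interval with +1.5 mmHg and, lower in the sequence, with +1.0 mmHg.

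**The concern.** The limit and the loss rate are two of the inputs that anyone checking the sample size must use, and as printed neither agrees with the rest of the plan.

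- **Limit.** Section 8.1 fixes which arm is subtracted from which, which sign is good and which confidence limit is used. That leaves no convention under which -2 is a non-inferiority margin. It would be a requirement of superiority by more than 2 mmHg.
- **Loss.** The step from 45 to 50 is attributed to subjects falling outside a population that, by definition, nobody randomized falls outside. The loss that can reduce the data is missing IOP, and the sizing text does not mention it.

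At stake is whether the justification can be reproduced and understood. The number randomized and the analysis do not depend on it.

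**Working it through.** **Inputs.** SD 3.0 mmHg, one-sided alpha 0.05, 45 evaluable and 50 randomized per group (Protocol 8.1, SAP 3.3); limit -2 (Protocol 8.1) or 2 (SAP 3.3); tested threshold 1.5 with a two-sided 95% interval (Protocol 8.4, SAP 4.3). The documents state no true difference δ. I take δ = 0 and then vary it.

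**Formula.** With limit M and n per group, SE = 3.0 × √(2/n), df = 2n − 2 and noncentrality = (M − δ)/SE. Power is the probability that a noncentral t variable exceeds the one-sided critical value.

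**1. The plan's own figure, M = +2.** At n = 45, SE = 3.0 × √(2/45) = 0.632 and the noncentrality is 2/0.632 = 3.16. Power is 93.2% (93.5% by the normal approximation). At n = 50, SE = 0.600 and power is 95.2%. Power of 90% needs 40 per group. The claim of at least 90% at 45 therefore reproduces with +2.

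**2. The printed limit, M = −2, n = 45.** The critical value on 88 df is about 1.662, so the half-width is 1.662 × 0.632 = 1.051. The observed difference must be below −2 − 1.051 = −3.05 mmHg. With +2 it need only be below 2 − 1.051 = 0.95 mmHg.

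| True difference (H-1337 minus timolol) | Power with limit −2, n = 45 |
|---|---|
| 0 | 0.00009% (8.6 × 10⁻⁷) |
| −1 | 0.07% |
| −2 | 5% |
| −3 | 47% |
| −4 | 93.2% |

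At n = 50 and δ = 0 power is 3.6 × 10⁻⁷. The stated power returns only if H-1337 is truly 4 mmHg better than timolol.

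**3. The loss allowance.** 45/(1 − 0.10) = 50, so the division is right. With ITT defined as all randomized, the share outside ITT is 0% and 45/(1 − 0) = 45. The figure of 50 follows only if the 10% describes some other loss.

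**4. What the corrected sizing sentence still does not cover.** The primary test uses 1.5 mmHg and a two-sided 95% interval, equivalent to one-sided 0.025. With δ = 0 and SD 3.0, the noncentrality at n = 45 is 1.5/0.632 = 2.37 and power is 65%. At n = 50 it is 1.5/0.600 = 2.50 and power is 70%. These are powers at one time point. The first step of the hierarchy requires success at all 7 time points (Protocol 8.4) or all 9 (SAP 4.3), so its power cannot exceed the single-time-point value under these assumptions.

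**The case against.** The best reply is that nothing depends on the minus sign. SAP 3.3 prints 2 mmHg, the SAP states that its variables and methods supersede the protocol's, the synopsis gives 2.0 mm Hg, and every threshold actually tested is positive. That stands, and it is why the point is minor. It does not make the protocol sentence right: 8.1 contradicts itself within two paragraphs.

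A reader might infer that the power claim is impossible. The documents do not support that. They state no true difference, and with a true advantage of 4 mmHg the power under −2 is again 93.2%. The claim fails at equal efficacy, which is an assumption, though the natural one for a non-inferiority design.

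A reader might also want SAP section 5 corrected because it reports the protocol's limit as 2. Once the protocol reads +2, that sentence is accurate as it stands.

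On the 10%, the sponsor could say that the sentence is a carry-over, since the SAP's summary of changes records that ITT was redefined in version 2.0. That is plausible, but the current texts still conflict. Nor would it be right to recast the 10% simply as subjects lacking Day 28 IOP. The primary analysis also uses Day 1 on-treatment time points in a longitudinal model with a subject effect, so a subject missing Day 28 can still contribute.

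**Conclusion.** Both inconsistencies are in the current text. The limit in Protocol 8.1 has the wrong sign under that section's own rule. At equal efficacy, SD 3.0 and one-sided 0.05, the printed value gives power of about 0.00009% at 45 per group, where +2 gives 93.2%. The 10% allowance in Protocol 8.1 and SAP 3.3 is set against a loss that Protocol 8.3 and SAP 3.4.2 make zero.

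Two stronger conclusions do not follow. The trial does not in fact require superiority by 2 mmHg, because no decision rule uses −2. And 50 per group is not shown to be too many: the allowance is mislabelled, and missing IOP that is not imputed is a real reason to randomize more than 45.

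Correcting the sign should not be taken as confirming the power of the primary test. SAP section 5 discloses that 2 was used for sizing and 1.5 and 1 for testing, but does not give the effect on power: about 65% at 45 and 70% at 50 per group for one time point, assuming no true difference and SD 3.0. Severity: minor.

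**What to change.** 1. In Protocol 8.1, change the limit from −2 to +2 mmHg. SAP section 5 then needs no correction on this point.
2. In Protocol 8.1 and SAP 3.3, replace the reference to ITT eligibility with a statement that 10% of subjects are expected to have no evaluable IOP at a given primary time point, with missing values not imputed. Keep 50 randomized and about 45 evaluable per group per time point. The sponsor should confirm that this is what the 10% is meant to cover.
3. In both sections, add that the power of at least 90% refers to a 2 mmHg limit at one-sided 0.05, and give the figure for the tested criterion alongside it: about 65% at 45 and 70% at 50 per group, for 1.5 mmHg with a two-sided 95% interval at one time point, no true difference and SD 3.0.

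The cost is wording in two documents and a less favourable stated power. The sample size, the analysis populations and the tests stay as they are.

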8.2 Statistical Methods

Continuous and ordinal measures will be summarized by descriptive statistics (n, mean, standard deviation, median, minimum and maximum values). Qualitative measures will be tabulated by counts and percentages. Selected safety measures may be summarized by the use of shift tables. Summary tables will show the data for each time point (visit and/or time of day as appropriate) and will display the observed and change from baseline value. In addition, percentage change from baseline will be summarized for IOP measurements.

Baseline is defined as the last non-missing measurement prior to first IP administration.

A statistical analysis plan will be finalized prior to unmasking the treatment assignments.

An analysis of results will be conducted when the database has been locked and the treatment assignments have been revealed. No interim analyses are planned.

8.3 Subject Population(s) for Analysis

All subjects who receive IP and at least one dose will be evaluable for the safety analysis. For efficacy considerations, the primary analysis population will be the intent-to-treat (ITT) population. All randomized subjects will be evaluable for the ITT analyses. Subjects who receive study medication, satisfy pre-randomization inclusion/exclusion criteria, and who complete at least one on-therapy study visit will be evaluable for a per protocol (PP) population analysis. Individual subject visits and data points that do not satisfy protocol criteria may be excluded from PP analyses. Evaluability will be determined prior to unmasking of treatment assignments.

8.4 Significance and Adjustment for Multiple Comparisons

Change from Baseline in IOP (mmHg) at Day 28 and Day 1 (on-treatment time points) in the study eye is the primary efficacy endpoint. It will be summarized by timepoint and treatment group in the ITT population primarily and in the PP population secondarily. The differences between treatments (H-1337 vs Timolol) will be calculated for each H-1337 treatment group. A timematched longitudinal model adjusting for baseline and including a random effect for subject will be used to calculate the LSmean, SE, and 2-sided 95% CI for the between treatments differences. To account for the multiple comparisons of the primary endpoints, adjustment for multiplicity will be fulfilled by using a hierarchical testing, based on a fixed-sequence procedure defined in

Table 3. First, the primary endpoint is tested for non-inferiority at all 4 time points at Day 28 (excluding +12 hours) and all 3 on-treatment time points at Day 1 (excluding +12 hours) for the first pre-defined Group comparison listed in Table 3. If the upper limit of the 2-sided 95% CI of the difference between H-1337 and Timolol is strictly lower than the value 1.5, then non-inferiority is concluded. If non-inferiority is concluded at the 7 timepoints, then testing of the second listed Group Comparison in Table 3 can take place at the 2-sided alpha level of 0.05. Otherwise, non-inferiority cannot be concluded and no further formal testing takes place. The same sequential approach is then applied to the remaining endpoints listed in Table 3.

Table 3 Pre-defined Sequence for Hierarchical Testing

Order	Group Comparison	Non-Inferiority Criteria
1	H-1337 1.0% Ophthalmic Solution b.i.d. vs	1.5 threshold at all 7 time points
	Timolol 0.5% Ophthalmic Solution b.i.d	
2	H-1337 0.6% Ophthalmic Solution b.i.d vs	1.5 threshold at all 7 time points
	Timolol 0.5% Ophthalmic Solution b.i.d	
3	H-1337 1.0% Ophthalmic Solution q.a.m. vs	1.5 threshold at all 7 time points
	Timolol 0.5% Ophthalmic Solution b.i.d	
4	H-1337 1.0% Ophthalmic Solution b.i.d. vs	1.0 threshold at 5 or more time points
	Timolol 0.5% Ophthalmic Solution b.i.d	
5	H-1337 0.6% Ophthalmic Solution b.i.d vs	1.0 threshold at 5 or more time points
	Timolol 0.5% Ophthalmic Solution b.i.d	
6	H-1337 1.0% Ophthalmic Solution q.a.m. vs	1.0 threshold at 5 or more time points
	Timolol 0.5% Ophthalmic Solution b.i.d	

8.5 Accountability Procedure

To reduce the incidence of missing data, sites and subjects will be trained in methods to encourage continued participation to maximize the completion rate and overall quality of the trial. There are no plans to impute values for missing data. With regard to the primary efficacy variable, IOP, there are steps taken in the procedure for collecting these data that minimize the likelihood of spurious data.

8.6 Deviation Reporting

Any deviations from the statistical plan enumerated in the final statistical plan will be described and justified in the clinical study report.

